**Methodology (cont.):**

After being enrolled and randomized into the study, subjects will be sent home with a kit containing a bottle filled with either Merlin (active) or the 10% ethanol placebo solution and a packet of foam-tipped applicators sufficient to apply three (3) study treatments (nine (9) applications). The subject will be instructed to contact the clinic by telephone at the first signs and/or symptoms of a recurrent herpetic episode (Stage 0, prodrome, Stage 1, erythema, or Stage 2, papule/edema). The lesion and lesion stage then will be confirmed by telephone interview with the subject. Subjects reporting either a Stage 1 or Stage 2 lesion will be instructed to begin treatment immediately, thereby initiating the Treatment Phase of the study. Subjects reporting only Stage 0 symptoms, i.e. no visible signs of a cold sore lesion, will be instructed to monitor their lesion and to call the clinic immediately upon observing any early visible signs of a cold sore, i.e. redness or swelling, representing a Stage 1 or Stage 2 lesion. Once the subject calls in and confirms by telephone interview that their lesion has reached Stage 1 or 2, they will be instructed to begin treatment immediately. The subject will be told to continue treatment for the remainder of the day with the treatment schedule outlined above, and to continue to treat with a set of three (3) applications, three (3) times each day, for a total of twelve (12) treatments resulting in thirty-six (36) applications in total. The subject also will be instructed to return to the clinic within 24 hours of the initial treatment for evaluation of the stage of the herpetic lesion.

Subjects will report daily for a minimum of 3 consecutive days, with the last clinic visit at the time of complete healing (Stage 7 - normal skin) or at 14 days, whichever is earlier. Subjects will be contacted by phone, for a safety assessment, 2 weeks after they complete the Treatment Phase of the study.

**Number of Subjects:** Approximately four hundred and fifty (450) subjects will be enrolled into the study, 225 into the active treatment group and 225 into the placebo treatment group. At least 75 subjects in the active treatment group, and 75 subjects in the placebo treatment group, will enter the Treatment Phase of the study and administer treatments.

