### 7.2.3 Entry into Study Treatment Phase

If a subject has met all the inclusion and exclusion criteria described in Section 5.3, and has a herpes labialis lesion in Stage 1 or Stage 2, the subject will then be allowed into the Treatment Phase of the study and instructed to open the Treatment kit containing the study material and begin treatment. The subject will be asked to schedule their Visit Day 1 clinic visit for later that day, if possible; otherwise the visit must be scheduled as early as possible the following day anytime within 24 hours of the time at which a subject calls and is allowed to enter the Treatment Phase of the study.

A subject who does not meet one or more of the Inclusion Criteria (Section 5.3.1), or certain Exclusion Criteria (specifically Treatment Phase Exclusion Criterion #1 - #5; Section 5.3.2) may still be eligible for continuing in the study. Those subjects will be instructed that they cannot be entered into the Treatment Phase of the study at that time, but must wait until their next outbreak at which time they can call in again to see if they qualify to begin the study treatment. The list of those criteria where subjects who do not meet those criteria can still participate in the study, but must defer their entrance into the Treatment Phase until their next cold sore recurrence, is provided below:

- The subject reports a lesion stage later than Stage 2 (Treatment Phase Inclusion Criterion #1).
- A female subject is not using a medically acceptable form of birth control (Treatment Phase Inclusion Criterion #2). In this instance, the subject will be instructed to return to the clinic for another pregnancy test. Once that test is shown to be negative, the subject will be told to resume proper contraception and can then call in again at the next lesion outbreak.
- The subject does not have immediate access to the clinical trial material kit (Treatment Phase Inclusion Criterion #3). In this case they will be asked to call again when he or she has the kit at hand. At the time of their second phone call they also will be asked again about the stage of their lesion to be certain that the lesion has not progressed beyond Stage 2.

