#### **7.2.4 Drug Administration**

Each subject, upon entering the Treatment Phase of the study, will be instructed to treat their lesion immediately using the solution and single-use applicators in the Treatment kit. The subjects, according to the randomization scheme, will begin self-administration of the applications of either Merlin or placebo solution. Treatment Day is the first day of treatment for all subjects.

At the time of the subject's call to enter the Treatment Phase of the study, the clinic should review the method and schedule of treatment applications with the subject.

For the first and all subsequent treatments, each subject will administer three (3) applications of Merlin or placebo, depending upon how a subject has been randomized, performed within a time period of 40 minutes or less, while allowing time for the solution to dry on the lesion between applications. A total of twelve (12) Merlin or placebo treatments, i.e. thirty-six (36) applications, will be administered over the ensuing 96 hours (4 days) from the time of the first treatment. On each day, treatments will be administered six (6) hours apart ( $\pm$  1 hour), with a maximum of three treatments each day. The first treatment will be administered on Treatment Day (Day 0), and then repeated at 6 ( $\pm$  1 hour) and 12 hours ( $\pm$  1 hour) after the first treatment, time permitting.

Subjects who, upon self-examination outside of the clinic, or upon evaluation in the clinic, are found to have herpetic lesions that have reached the ulcer/soft crust stage (Stage 4) should be instructed to discontinue all remaining treatments. If the observation of the lesion reaching Stage 4 is made by the subject outside of the clinic, the subject should call into the clinic as soon as possible after making this observation to confirm the accuracy of their assessment and to report the event.

Subjects who are unable to begin treatment for any reason, aside from those listed in Section 7.2.3, are to be discontinued from the study; those subjects are to return to the clinic to turn in their clinical trial materials and are not to be followed for safety or efficacy. Subjects, though, who are able to complete any part their treatment, even only a single application of the solution to the face, are to continue to participate in the study as planned, including appearing for all safety and lesion assessment clinic visits.

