### 10.3.2 Efficacy: Modified Intent-to-Treat (MITT) Population

All subjects who have been entered into the Treatment Phase of the study will be included in the MITT population. It is considered a “modified” intent to treat population in that it does not include all randomized subjects but includes only those randomized subjects who access their treatment, i.e., are told to open their kit. The MITT population will be used as the primary analysis population. A subject will be included in a treatment group for analysis based upon the treatment to which he or she has been assigned.

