## 10.7 Efficacy Analysis

The efficacy analysis will be performed on both the MITT and the efficacy evaluable populations. For all duration endpoints the following matrix will be used for analyses:

Population	Analysis	Description	Methods
MITT	Main Analysis	Impute duration for subjects who drop out prior to healing with a duration of 336 hours (14 days x 24 hours).	Hodges-Lehmann estimation methods; Wilcoxon rank sum test to compare arms
	Sensitivity Analysis	Subjects who drop out prior to healing will be considered censored.	Kaplan-Meier estimation methods; Log-rank test to compare arms
EE	Main Analysis	No imputation required since these are complete cases.	Hodges-Lehmann estimation methods; Wilcoxon rank sum test to compare arms

For all endpoints on the occurrence of prevention of progression, counts and percentages will be summarized, and chi-square tests, or Fisher's exact test will be used to compare arms, as appropriate. Fisher's exact tests will be used if any of the expected cell counts in the Rx C crosstabulations are less than 5.

For size endpoints, means, medians, standard deviations and ranges will be summarized. T-tests will be used to compare arms if the sizes are approximately normally distributed, or Wilcoxon rank sum tests will be used if the sizes are markedly non-normally distributed.

For the severity endpoints, counts and percentages will be summarized, and Cochran-Mantel-Haenszel tests will be used to compare the arms.

In order to assess whether there are differences among centers in treatment effects, a Cox proportional hazards model analysis of the duration of herpetic episode will also be performed for the primary duration endpoint and for both the MITT and EE populations. The model will include terms for treatment, center, and treatment by center interaction. A test will be performed to test for the significance of the interaction. This test will be conducted at the 0.10 level of significance. If the interaction is found to be significant, estimates of treatment effect will be provided by center, as well as overall.

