### 7.1.2 Modified Intent-to-Treat (MITT) Population

All subjects who have been entered into the Treatment Phase of the study will be included in the modified intent-to-treat (MITT) Population. It is considered a “modified” intent to treat population in that it does not include all randomized subjects but includes only those randomized subjects who access their treatment, i.e., are told to open their kit. A subject will be included in a treatment group for analysis based upon the treatment to which he or she has been assigned; imputation on the primary endpoint only is planned for the MITT Population – see section 7.13. The MITT Population will be used as the primary analysis population and for all efficacy analyses.

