## **7.2 General Analysis**

All statistical tests will be done using two-sided tests and a Type I error rate of 0.05.

Data listings will be based on all subjects in the Safety Population.

Continuous variables will be summarized using descriptive statistics, specifically the mean, median, standard deviation, minimum and maximum values. Categorical variables will be summarized by frequencies and percentages.

The primary analyses will compare the active treatment group to the placebo control group. Aside from any placebo effect, there should be no efficacy associated with the placebo solution. In addition to the overall analyses, all statistical comparisons will be performed with the subjects stratified based on whether they were treated at erythema (Stage 1) or papule/edema (Stage 2). Inference testing will be completed on efficacy data to compare the groups. Safety data will be summarized with descriptive statistics, but no inference testing will be completed to compare the groups statistically.

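### MITT admits every subject told to open the kit, but those who never start treatment are not followed, so their durations are scored 336 h on secondary endpoints or left undefined on the primary

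*Protocol*

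**What the plan says.** **Entry.** Under Protocol 7.2.3, a caller who meets the criteria and has a Stage 1 or 2 lesion qualifies by telephone: "the subject will then be allowed into the Treatment Phase of the study and instructed to open the Treatment kit". The first treatment is then self-administered, typically at home.

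**Population.** SAP 7.1.2 states: "All subjects who have been entered into the Treatment Phase of the study will be included in the modified intent-to-treat (MITT) Population". Protocol 10.3.2 says the same and explains that MITT "includes only those randomized subjects who access their treatment, i.e., are told to open their kit". MITT is the primary analysis population. The Safety Population (Protocol 10.3.1, SAP 7.1.1) additionally requires that some treatment was self-administered, so the plan itself separates entering from treating.

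**Follow-up.** Protocol 7.2.4 discontinues subjects who cannot begin treatment, other than the deferrals listed in 7.2.3, and says they "are not to be followed for safety or efficacy". Anyone who makes even one application stays in the study and attends all visits.

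**Scoring.** For the MITT main analysis of all duration endpoints, Protocol 10.7 says: "Impute duration for subjects who drop out prior to healing with a duration of 336 hours". SAP 7.13.1 and 7.13.5 repeat this. SAP Section 8 goes further and imputes any MITT duration that cannot be retrieved by query, with the unit printed as days. SAP 7.1.2, however, says imputation is planned for the primary endpoint only.

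**Reporting and target.** SAP 7.2 states: "Data listings will be based on all subjects in the Safety Population". The synopsis counts at least 75 subjects per arm who "will enter the Treatment Phase of the study and administer treatments". Protocol Sections 4 and 5.1 count entry alone.

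**The concern.** Read together, these sections place a subject in the primary population and then stop anyone from observing that subject's lesion. No section removes such subjects from MITT or says how to score them.

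Where the 336 h rule does reach them, it gives the worst possible duration to people exposed to neither solution. That dilutes a real effect, and any chance difference between arms in non-starters moves the estimate for reasons unrelated to treatment. Where the rule does not clearly reach them, as for the primary endpoint, whether they count becomes an analyst's decision that the plan does not make.

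Two smaller consequences follow. Subjects who never treated appear in no data listing, because listings are restricted to the Safety Population. And if the 75-per-arm minimum is met by entry alone, the trial can close with fewer than 75 treated subjects in an arm.

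**Working it through.** **The plan's own figure.** 14 days x 24 hours = 336 hours, as Protocol 10.7 states. The unit in SAP Section 8 would give 336 x 24 = 8,064 hours and is evidently a slip for hours.

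**What happens to a subject who entered but never applied anything, by analysis**

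- *Herpetic episode and complete healing, MITT main analysis.* All lesions count, aborted or classical. Both durations run from the beginning of treatment, which does not exist here, so the value is missing and not retrievable. SAP Section 8 then imputes 336 h. Protocol 10.7 and SAP 7.13.1 do the same if a non-starter counts as a dropout before healing. SAP 7.1.2 points the other way.
- *Primary endpoint, MITT main analysis.* Protocol 10.7.1 excludes aborted lesions, and Protocol 7.3.1 classes a lesion as classical from Stages 3, 4 or 5 at a lesion assessment. Without assessments the lesion is neither, so both inclusion and score are undefined.
- *MITT sensitivity analysis.* The subject would be censored with no time origin.
- *EE analysis.* Unaffected, because EE requires completed treatment.

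**Illustrative size, herpetic episode only.** The documents give no SD, placebo mean or never-treated rate, so all three are assumptions.

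Inputs from the sample-size section (Protocol 10.7.9, SAP 3): difference 41 h, p = 0.055, and 32 and 22 subjects (printed for the classical-lesion result and assumed here to apply to the episode result).

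- sqrt(1/32 + 1/22) = 0.277
- Using t on 52 df: 41 / 1.963 = 20.9 h; SD = 20.9 / 0.277 = about 75 h
- Using z: 41 / 1.919 = 21.4 h; SD = 21.4 / 0.277 = about 77 h

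Two set-ups were simulated with 75 per arm, a true difference of 41 h and 3,000 trials per scenario, using the two-sided 0.05 Wilcoxon rank sum test and the Hodges-Lehmann estimate (placebo minus Merlin). Set-up A: SD 75 h, placebo mean 200 h, durations held within 24-330 h. Set-up B: SD 77.1 h, placebo mean 180 h, held within 12-336 h. Never-treated subjects were set to 336 h.

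| Never-treated, Merlin / placebo | A: power (estimate) | B: power (estimate) |
|---|---|---|
| 0 / 0 | 90% (41 h) | 88% (42 h) |
| 2 / 2 | 86% | 86% (42 h) |
| 4 / 4 | 84% | 83% (40 h) |
| 4 / 1 | 74% (34 h) | - |
| 4 / 0 | - | 68% (33 h) |
| 0 / 4 | - | 95% (47 h) |

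Removing those subjects instead gave 88-89% power and 41 h in set-up A. In set-up B with no true effect, the test rejected in 5.5% of trials with 0/0, 3.1% with 4/4, 7.1% with 4/0 and 7.8% with 0/4. For scale, 4 of 75 is 5.3% of an arm. Simulation error is small: sqrt(0.74 x 0.26 / 3,000) = 0.008.

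**The case against.** **Section 7.2.4 may concern only callers who have not yet entered.** This is possible but not the natural reading. The section opens with subjects who have entered the Treatment Phase, exempts the 7.2.3 deferrals, and contrasts non-starters with those who apply once. On the other reading, entered non-starters have no stated handling at all, so the text still needs repair.

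**There may be almost none.** Before entry the subject must have the kit in hand and read out its number, must be able to attend within 24 hours, and is told to treat at once. This stands. With balanced small numbers the loss is modest, and the large figures need an imbalance.

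**Population counts by arm are already planned.** SAP 7.3 tabulates them, so a gap between MITT and Safety would show. This stands in part. Safety can also include people who treated without authorisation, so the difference is not an exact count of non-starters.

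**Keeping everyone told to open the kit is closer to intention-to-treat.** It is, but that principle needs outcomes, and the protocol does not collect them here. Following all entered subjects would also remove the contradiction, but it would still leave no start time for subjects who never treat.

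**Stronger readings to avoid.** A reader might infer that the primary endpoint will contain 336 h scores for untreated people. The documents do not direct that; they leave it undefined. A reader might also infer bias against Merlin. Assignment is double-blind and non-starting precedes any exposure, so imbalance would arise by chance and could favour either arm, as the 0/4 row shows. Finally, the power figures do not carry over to the primary endpoint.

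**Conclusion.** The inconsistency is real and should be resolved. Membership of the primary population is fixed by a telephone instruction, while observation depends on a first application, and nothing deals with subjects who fall between the two.

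The 336 h consequence is firmest for herpetic episode and complete healing, through SAP Section 8, and even there SAP 7.1.2 contradicts it. For the primary endpoint the defect is an undefined rule, and its effect is not quantified.

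The illustrated changes in power and estimate rest on an assumed number of non-starters, an SD back-calculated from one p-value, an assumed placebo mean and normal durations. They show that a few such records can matter, not that they will occur. A loss of about 5 to 6 percentage points at 4 per arm is the balanced case. An imbalance of 3 or 4 subjects moves the estimate by roughly 5 to 9 h in whichever direction it falls.

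**What to change.** 1. In Protocol 10.3.2 and SAP 7.1.2, define MITT as randomised subjects who entered the Treatment Phase and made at least one application, analysed as randomised. This is the line Protocol 7.2.4 already uses to decide who is followed. Because non-starting is decided before exposure and under blinding, the exclusion should not bias the comparison.
2. In the SAP 7.3 disposition table, add an explicit row by arm for subjects who entered but never treated.
3. In Protocol Sections 4 and 5.1, and in SAP 2.2 which repeats the entry-only count, align the 75-per-arm minimum with the synopsis, so that a subject counts once treatment has been administered.
4. While editing, reconcile the imputation scope in SAP 7.1.2 with SAP 7.13.1 and Section 8, and correct the unit in Section 8 to hours.

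The cost is a few sentences and one table row, with no new data collection. The downsides are that MITT becomes slightly smaller, moves one step further from full intention-to-treat, and relies on a first application reported by the subject. SAP 7.10 itself calls diary-based compliance unreliable.

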### **10.3.3 Efficacy Evaluable (EE) Population**

All subjects who have been entered into the Treatment Phase of the study were reported to have successfully completed treatment, and have been followed successfully until their lesion heals, or until 14 days, whichever is earlier, will be included in the efficacy evaluable population. Prior to breaking the study blind, study data will be reviewed to determine which subjects need to be excluded from the efficacy evaluable population. A subject will be included in a treatment group for analysis based upon the treatment actually administered, rather than the group to which he or she has been assigned. For example, a subject who is randomized to receive a placebo treatment but inadvertently receives an active treatment will be included in the group receiving an active treatment, and vice versa. Only actual observations will be included in the analyses; no imputation for missing data will be performed.

## **10.4 General Methodology**

All statistical tests will be done using two-sided tests and a Type I error rate of 0.05.

Data listings will be based on all subjects in the safety population.

Continuous variables will be summarized using descriptive statistics, specifically the mean, median, standard deviation, minimum and maximum values. Categorical variables will be summarized by frequencies and percentages.

The primary analyses will compare the active treatment arm to the placebo control arm. Aside from any placebo effect, there should be no efficacy associated with the placebo solution. As a secondary analysis, all statistical comparisons will be performed with the treated subjects stratified based on whether they treated at erythema (Stage 1) or papule/edema (Stage 2).

## **10.5 Baseline Demographics**

Baseline demographic information will be summarized for the safety population. For continuous variables, summary statistics (mean, median, standard deviation, minimum, and maximum) will be provided. For categorical variables, the frequency and percent in each category will be presented.

## **10.6 Safety and Tolerability Analysis**

The safety analysis will be performed on the safety population. Assessment of safety and tolerability will be based on adverse events. Each AE will be graded with respect to its relationship to treatment using five categories: not related, unlikely, possible, probable, and highly probable. Each AE will also be graded on a three-point severity scale: mild, moderate, and severe. Adverse events will be coded by body system and preferred term using the MedDRA (Medical Dictionary for Regulatory Activities) dictionary.

The number and percentage of subjects experiencing adverse events will be tabulated for each treatment group by body system and preferred term. The number and percentage of subjects experiencing AEs will also be tabulated by relationship to drug treatment and by severity. If an AE is reported more than once for a subject, only the most related event will be counted in the analysis by relationship to drug treatment. For the analysis by severity, if an AE is reported more than once for a subject, only the most severe event will be counted in the analysis.

